Title of the study:

The effect of personal protective aids on hypertension and diabetes in people exposed to high levels of air pollution

Date of the document:

January 1, 2021

The effect of personal protective aids on hypertension and diabetes in people exposed to high levels of air pollution

Background and Rationale
Study Aim 1
Study Aim 2
Ethical consideration
References

Study Site: Dalkhola, West Bengal, India

Background and Rationale:

Pollution is the largest environmental cause of disease and premature death in the world today. Nearly 92% of pollution-related deaths occur amongst low-income and middle-income countries such as India. Diseases caused by pollution are most prevalent amongst minorities and marginalized at every income level. It disproportionately affects the poor and the vulnerable. Although more than 70% of diseases caused by pollution are non-communicable diseases, interventions against pollution are barely mentioned in the Global Action Plan for the Prevention and Control of Non-Communicable Diseases. Environmental agents are one of the risk factors for non-communicable diseases, especially cardiovascular diseases (CVDs) such as myocardial infarction and stroke.(1) Ambient noise and air pollution (fine particulate matter <2.5 mm – PM 2.5) represent the two most important environmental risk factors. Together, they contribute to over 75% of the disease and disability burden associated with known environmental risk factors, most importantly cardiovascular (CV) mortality and disability.(2) Short-term elevations in PM2.5 increase the relative risk of acute CV events by 1% to 3% within a few days. Longer-term exposures over several years increase this risk by a larger magnitude (~10%), which is partially attributable to the development of cardiometabolic conditions (e.g. hypertension and diabetes mellitus). As such, ambient PM2.5 poses a major threat to global public health.(3) There is enough evidence in support of an association between these environmental agents and CV risk factors, mainly hypertension and diabetes. India, a rapidly developing country, is one of the most heavily polluted countries in the world and has the highest burden of diseases due to environmental risks. (4) With an increase in pollution, strategies are needed to combat the health effects of pollution at an individual level.

Preliminary data shows that the use of personal protective aids (such as home air purifier, N-95 mask) can decrease systolic blood pressure and blood glucose in healthy individuals exposed to high levels of air pollution (5–11). A considerable body of evidence suggests that the environmental agents, like traditional cardiovascular risk factors, induce low-grade inflammation, oxidative stress, vascular dysfunction, and autonomic nervous system imbalance, thereby facilitating the development of diseases such as hypertension and diabetes. Through their impact on traditional risk factors and via additional novel mechanisms, environmental risk factors may have a much larger impact on CV events than currently appreciated (12). No

studies have examined the impact of personal protective aids on people with hypertension and diabetes. We therefore hypothesize that the use of personal protective aids can decrease systolic blood pressure in people with hypertension and decrease fasting blood glucose in those with diabetes. In addition to the enormous burden of air pollution, identifying strategies that can mitigate personal risk from pollution is of major public health importance considering the large number of people with hypertension and diabetes in India.

Given the current deficits in knowledge, we plan to conduct a randomized cross over study in Dalkhola, West Bengal to test the hypothesis that in people exposed to high level of air pollution, the use of personal protective aids will decrease systolic blood pressure in people with hypertension, and decrease blood glucose in people with diabetes.

Study Aim 1:

To compare the effect of personal protective aids on blood pressure in people with hypertension and blood glucose in those with diabetes

Hypothesis:

In people exposed to high level of air pollution, the use of personal protective aids (air purifier and personal mask) will decrease systolic blood pressure in people with hypertension and decrease blood glucose in people with diabetes.

Design and Method:

It will be a prospective, randomized cross over study in which participants will act as their own control. Ambient air pollution will be recorded in Dalkhola town in each ward/unit. Based on the recordings, the top 5 wards/units will be selected. Participants who live within 300m radius of the monitoring area of each ward/unit will be screened for hypertension and diabetes by community health workers (CHWs) who are trained to record blood pressure and blood glucose level by the investigators. After screening and obtaining informed consent, they will be randomized to either intervention arm or control arm. Both arms will be for 4 weeks duration and the blood pressure and blood glucose levels will be recorded on Day 0, end of week 2 and end of week 4. Intervention group participants will be given an indoor air purifier (to be used daily for 12 hours between 8 PM and 8 AM) and a washable N95 mask (to be used when the participant is outdoors). The control arm participant will receive an identical air purifier, but without the filter. Similarly, the control arm participant will continue to wear the N-95 mask during the control phase, with the N-95 filter removed by the health worker. This will ensure blinding of the participant. All blood pressure and blood glucose measurements will be made by a health worker who is blinded to the study group of the participant. At the end of the first 4 weeks, there will be a washout period of 2 weeks in which the participants will return to their usual state. The participants who were initially in the intervention arm will be placed in the control arm and vice versa. 15% of the participants will be randomly selected for indoor air

pollution monitoring during each arm. We will have a run-in period for 2 day for the intervention – using air purifier and wearing N95 mask. Participants who show good adherence will be recruited in the study.

Inclusion Criteria:

Hypertension arm

- 1. Individuals age 18-70 years old with systolic blood pressure between 130-160 mmHg, regardless of medication use
- 2. Stable hypertension for the past 3 months with no medication changes
- 3. No planned medication changes for the duration of the study
- 4. Exposure to outdoor air pollution above a certain threshold (pollution levels will be measured using AirVeda devices)
- 5. Individuals who sleep in a closed space (such as a bedroom) for minimum of 6 hours/daily.
- 6. Use of gas (LPG)/electricity for cooking purposes

Diabetes arm

- 1. Individuals age 18-70 years old with fasting blood glucose between 126-180 mg/dL, regardless of medication use
- 2. Stable diabetes for the past 3 months with no medication changes
- 3. No planned medication changes for the duration of the study
- 4. Exposure to outdoor air pollution above a certain threshold (pollution levels will be measured using AirVeda devices)
- 5. Individuals who sleep in a closed space (such as a bedroom) for minimum of 6 hours/daily.
- 6. Use of gas (LPG)/electricity for cooking purposes

Exclusion Criteria

- 1. Unwilling to participate
- 2. Unstable blood pressure and/or blood glucose level requiring frequent medication changes
- 3. Individual suffering from a physical or mental illness that precludes active study participation
- 4. Current smoker
- 5. Planned vacation/absence from the study site
- 6. Patients with life expectancy < 12 months
- 7. Pregnant patients

Screening, recruitment and randomization:

Participants from the selected ward will be screened by the community health worker for hypertension and diabetes. For those who are diagnosed with HTN/DM, she will record the BP/BG level during the first home screening visit. The screening will be based on form 0 which has been attached with the protocol in the appendix. Participants who were never diagnosed with HTN/DM but had elevated BP/BG level during the first visit will not be included in the study. At the time of recruitment, CHWs will fill out form 1 of the screening questionnaire, which has also been attached. She will also obtain informed consent, which will be explained and printed in the local language. Participants will be randomized using sealed, opaque envelopes.

Sample size and power calculation:

128 participants (calculated with 80% power; alpha level of 0.05; to detect the difference of 2mmHg; assumed SD 8) with hypertension will be randomly exposed to one of two arms for 4 weeks, followed by exposure to the other arm.

Similarly, 33 participants (calculated with 80% power; alpha level of 0.05; to detect the difference of 10mg/dL; estimated SD 20) with diabetes will be randomly exposed to one of two arms for 4 weeks, followed by exposure to the other arm.

	2 mmHg	3 mmHg	4 mmHg
SD=6	73	33	20
SD=7	98	45	26
SD=8	128 paired observations	58	33

	10 mg/dL	15 g/dL	20 mg/dL
SD=15	20	10	7
SD=17	25	12	8
SD=20	33 paired observations	16	10

Intervention group:

Intervention arm will be for 4 weeks. Blood pressure and/or blood glucose will be recorded on day 0; end of week 2 and end of the intervention. Participants in the intervention group will be asked to use an indoor air purifier (Atlanta Healthcare 7-Stage 43-Watt Air Purifier) daily for 4 weeks between the hours of 8 PM and 8 AM. The purifier will be placed in their bedroom or in the room where participants sleep at night. When the participants are outdoors (commuting, working outdoors, running errands, etc.), they will be asked to use a N95 mask (PureMe Reusable N95 Anti-Pollution Mask). It is a reusable mask which can be washed by the participants. Every 2 weeks, the filter of the mask will be replaced, and the filter of the indoor purifier will be washed.

Washout period:

At the end of either control or intervention arm, participants will have a washout period of 2 weeks, after which participants will be crossed over to the other group for the subsequent 4 weeks. For example, after Participant AB is in intervention arm for 4 weeks, he/she will then have a wash out period of 2 weeks in which they will return to their usual state of living. At the end of the washout period, the participant AB will be put in the control arm for 4 weeks.

Control group:

Control arm will be for 4 weeks. Blood pressure, blood glucose and indoor air pollution level will be recorded similarly as in the intervention group on day 0, end of week 2 and week 4. The participant will be provided an air purifier and a N-95 mask (of the same manufacturer), with the filter removed. At the end of two weeks, the health worker will make dummy adjustments to the mask and indoor air purifier, to maintain blinding of the participant.

Study outcomes:

Primary:

- 1. Absolute decrease in systolic blood pressure for people with hypertension using air purifier and facemask
- 2. Absolute decrease in fasting blood glucose for people with diabetes using air purifier and facemask

Data Collection:

All data in the screening questionnaire will be entered by the data entry operator in predesigned database forms in a RedCAP database.

Analysis:

Analysis will be done on an intention to treat basis. Marginal (GEE) models will be used to analyze the data.

Measurements and definitions:

Pollution measurement and recording:

Given that there is no pollution monitoring unit in or near Dalkhola, we plan to directly record the pollution level in Dalkhola. We will be using Airveda Outdoor PM 2.5, PM 10 air quality monitor to record ambient air pollution levels. Ambient (Outdoor) air pollution level recording will include: Average PM 2.5 level, Average PM 10 level, Peak PM 2.5 level, Trough PM 2.5 level, AQI (Air quality index), Average temperature and Average humidity. Indoor air pollution level will be recorded using Airveda Smart Air Quality Monitor. Because the personal air pollution level depends on the indoor/outdoor ratio, which is beyond the scope of this study, we will assume that it is the same for all participants and thus, will record the indoor air pollution level at the site where participants sleep at night.

Blood pressure measurement:

The blood pressure will be measured using an electronic BP machine (Omron HEM- 8711). The average of the last two of three left-arm blood pressure measurements after a minimum of 5 minutes of rest with the participants seated with feet on the floor and arm supported at heart level will be used.

Blood glucose measurement:

The capillary blood glucose levels will be measured using handheld blood glucose meters (Accucheck Performa). The participant is educated on the importance of fasting at the initial visit and fasting status will also be confirmed prior to a measurement. The finger prick will be made (sterile lancet after swabbing with spirit swab) on the left ring finger and capillary blood glucose will be measured and recorded.

Study Aim 2:

To understand the knowledge, attitude and perception of people with hypertension and/or diabetes regarding air and noise pollution and its health effects.

Design and Method:

The planned study consists of focus group discussions designed to qualitatively assess knowledge, attitude and perception of people with hypertension and/or diabetes regarding air and noise pollution and its health effects in India. Participants will include about 40 adults, between the ages of 18 and 70, from a semi-urban community in the town of Dalkhola, Uttar Dinajpur district, West Bengal, India. Each semi-structured focus group will consist of 6 to 8 participants and is expected to last around 45 to 60 minutes. We plan to have a total of 6 (*n*=36-48) group discussions. To facilitate discussion, we will use a semi-structured guide that employs key concepts from the literature. Sessions will be led in the local language, Bengali, and will be digitally recorded. Recordings will be translated to English, and transcribed verbatim in English.

Focus groups will be performed in Dalkhola, at a local community hall that is accessible and convenient for all participants. The focus group leaders will be one of the investigators ([name]/[name]), with assistance from the study coordinator.

Participant recruitment:

We will be recruiting 2 sets of individuals: 1) Participants who were enrolled in the personal protective aids study and 2) Participants from the same ward/unit who were not enrolled in the personal protective aids study.

Inclusion criteria:

1. Individuals with hypertension and/or diabetes, between the ages of 18 and 70

Exclusion criteria:

- 1. Individuals who are deemed unable to actively participate in the focus group discussions
- 2. Individuals who refuse consent

Basis for sample size of 36-48:

We want to conduct 6 focus group discussions, with the composition as enclosed. We believe this number will allow the representation of sufficiently diverse perspectives on hypertension and diabetes. Each focus group discussion will have 6-8 participants, resulting in an estimated size of 36-48 participants. Since the study is primarily qualitative, no sample size calculations are required as we are not powering the study for any quantitative outcomes.

Procedure:

After written/verbal informed consent is obtained, a trained interviewer will initiate the focus group discussion, based on the guide (below). A second person in the room will take notes on nonverbal cues. The entire discussion will be recorded for data analysis and study of non-verbal cues. At the conclusion of the focus group, all subjects will be given Rs 100/- as a token of appreciation.

The planned 6 groups are as follows-

Participants from personal protective aids study:

- 1) High adherence to DM and/or HTN medicines (Men and women)
- 2) Low adherence to DM and/or HTN medicines- Women
- 3) Low adherence to DM and/or HTN medicines- Men

Participants from the same ward/unit who were not a part of personal protective aids study:

- 4) High adherence to DM and/or HTN medicines (Men and women)
- 5) Low adherence to DM and/or HTN medicines- Women
- 6) Low adherence to DM and/or HTN medicines- Men

* Low adherence includes participants who have not sought a physician's opinion for management of their hypertension and/or diabetes

Analysis:

Qualitative data will be collected, transcribed, and associated with quantitative data such as demographics and treatment adherence. Using qualitative description analysis, researchers will evaluate responses independently to identify patterns, themes, important features and commonalities and differences. They will also develop codes for the data relevant to study variables. MAXQDA software will be used to manage data and assist in code development. The investigators will discuss and resolve coding discrepancies. Quantitative data will be described by frequencies, proportions, means or medians, and focus group themes will be compared using Pearson chi-squared test or Fisher exact test.

Reference:

- Hänninen Otto, Knol Anne B., Jantunen Matti, Lim Tek-Ang, Conrad André, Rappolder Marianne, et al. Environmental Burden of Disease in Europe: Assessing Nine Risk Factors in Six Countries. Environ Health Perspect. 2014 May 1;122(5):439–46.

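### Does the 2-day run-in with the intervention devices make the two period baselines unequal and so bias the crossover comparison?

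*Combined protocol and SAP*

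**What the plan says.** The run-in appears at the end of Design and Method for Study Aim 1: "We will have a run-in period for 2 day for the intervention", using the purifier and the mask. It is an adherence screen: "Participants who show good adherence will be recruited in the study". Filter removal is described only for the control condition ("The control arm participant will receive an identical air purifier, but without the filter"), so the natural reading is that filters are fitted in the run-in. The text does not say so outright, and gives no interval between the end of the run-in and Day 0.

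Between periods, "there will be a washout period of 2 weeks in which the participants will return to their usual state". No second run-in is described. In each period "blood glucose levels will be recorded on Day 0, end of week 2 and end of week 4", and blood pressure follows the same schedule.

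The Study outcomes section gives the first primary outcome as "Absolute decrease in systolic blood pressure for people with hypertension using air purifier and facemask", and words the glucose outcome in the same way. Neither names a reference value or time point. Apart from the intention-to-treat principle, the Analysis section says only "Marginal (GEE) models will be used to analyze the data"; it lists no model terms.

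**The concern.** In a crossover with a baseline reading in each period, one wants the two baselines taken under like conditions. Here they may not be. If filters are fitted in the run-in and Day 0 follows at once, the period-1 baseline may already be lowered by two days of treatment, while the period-2 baseline is taken after two untreated weeks. Any change measured from the period-1 baseline would then be too small.

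The outcome wording adds to the worry. A decrease while using the devices could be read as a before-after change within the intervention phase. On that reading the loss does not cancel, because it falls on everyone who starts on the intervention. The Analysis section does not exclude this, since it neither names a period term nor says how Day 0 enters the model. At stake would be an understated effect in a trial planned around small differences: 2 mmHg and 10 mg/dL.

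**Working it through.** **Inputs from the protocol** (Sample size and power calculation): hypertension, planned difference E = 2 mmHg, SD 8, N = 128; diabetes, E = 10 mg/dL, SD 20, N = 33; power 80%, alpha 0.05.

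**The plan's own figures.** With the SD read as that of the within-person difference, a two-sided paired t-test at 80% power needs 128 and 34 pairs. The plan states 128 and 33; power is 80.2% at 128 and 79.5% at 33. Two independent samples would need 252 and 63 per arm. The trial is therefore sized on the within-person difference between conditions.

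**Assumption.** The documents give no size for a 2-day effect. Let the run-in lower the period-1 Day 0 value by r = f × E, with f from 0 to 0.5. Then r is 0-1 mmHg or 0-5 mg/dL.

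**Outcome A: intervention minus control, change from each period's Day 0.** Let n1 participants start on the intervention and n2 on control.

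- Intervention first: the intervention decrease loses r and the control decrease is unaffected, so the contrast is E − r.
- Control first: the control decrease loses r and the intervention decrease is unaffected, so the contrast is E + r.
- Simple average: E − r(n1 − n2)/N. With n1 = n2 this equals E.
- With a period term, the estimate is the mean of the two sequence means: [(E − r) + (E + r)]/2 = E, whatever the split.

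With unequal sequences and no period term, the shift is r(n1 − n2)/N. The standard errors are 8/√128 = 0.71 mmHg and 20/√33 = 3.48 mg/dL.

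| Group, split | f | Shift | % of E | % of one SE |
|---|---|---|---|---|
| SBP, 70/58 | 0.25 | 0.5 × 12/128 = 0.047 mmHg | 2 | 7 |
| SBP, 70/58 | 0.50 | 1.0 × 12/128 = 0.094 mmHg | 5 | 13 |
| Glucose, 19/14 | 0.25 | 2.5 × 5/33 = 0.38 mg/dL | 4 | 11 |
| Glucose, 19/14 | 0.50 | 5.0 × 5/33 = 0.76 mg/dL | 8 | 22 |

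These splits are illustrative. No blocking is stated; under simple 1:1 randomisation an imbalance at least this large has probability 0.33 (128) and 0.49 (33). Either sequence is equally likely to be the larger, so n1 − n2 has expectation zero. The shift dilutes the effect in one case and inflates it in the other.

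Precision hardly moves either. With equal sequences and no period term, the SD becomes √(SD² + r²). For SBP it rises from 8 to 8.02-8.06, and power goes from 80.2% to 80.0-79.5%. For glucose it rises from 20 to 20.16-20.62, and power goes from 79.5% to 78.9-77.1%.

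**Outcome B: only week-2 and week-4 values compared.** Day 0 does not enter, so the shift is 0. This takes the run-in effect to have gone by week 2, which is at least two weeks after the run-in ends and so at least as long as the plan's own washout.

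**Outcome C: before-after decrease in the intervention phase only.** With equal sequences, half the participants lose r, so the mean decrease is understated by r/2. For SBP this is 0, 0.25 or 0.5 mmHg at f = 0, 0.25 or 0.5, that is 0-25% of 2 mmHg.

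**Which outcome the plan intends.** Aim 1 is framed as a comparison. Design and Method makes each participant his or her own control. The sample size is in paired observations and reproduces only as a paired difference. The control phase has the same visits, and dummy device adjustments at two weeks. All of this points to A or B. Under C the control phase would have no role in the primary result.

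**The case for a change.** The strongest reply is that cancellation depends on things the plan does not write down: a between-condition outcome, and either balanced sequences or a period term. The outcome sentence names no comparator, the analysis is two sentences long, and sealed envelopes without stated blocking make unequal sequences quite ordinary. In the 33-person diabetes group the shift is relatively larger. A few sentences would settle the matter and would also prevent a baseline being chosen after the data are seen.

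Much of that is true as description. The run-in's filter status and timing, the reference for the decrease and the GEE terms are all missing detail. What does not follow is that the run-in puts the result at risk. For the contrast to move at all, five things must hold together: filters fitted, Day 0 soon after the run-in, change from Day 0 as the response, no period term, and unequal sequences. Even then the shift is at most about a fifth of a standard error under a deliberately generous assumption, and it has no preferred direction. The undefined reference value and model terms would be gaps with or without a run-in.

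It can also be said that the run-in gives control-first participants an early comparison with the filterless devices. The crossover exposes everyone to both versions anyway, the purifier casing is identical, and the measurer is blinded. The documents give nothing from which to size any additional effect.

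**Conclusion.** No change is needed. The two period baselines may not be like for like, but any difference is common to both sequences and is therefore a period effect. In the contrast that the design and sample size point to, the bias is zero with equal sequences or a period term, and zero if only follow-up values are compared. Otherwise it is a chance shift of about 0.05-0.09 mmHg or 0.4-0.8 mg/dL for the splits shown, on an assumed run-in share of 25-50% that nothing in the documents supports; at a share near zero it disappears. The 0-25% understatement belongs only to a before-after reading that sets the control phase aside.

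What remains is detail that an analyst of a two-period crossover fills in as a matter of course: take the decrease as the within-person difference between conditions, and include period in the GEE. An additional reading before the run-in, a 2-week gap after it, or a filterless run-in would gain nothing for that contrast. The gap would cost each participant two weeks, and a filterless run-in would no longer test adherence to the filtered mask.

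### Individuals are randomised but the purifier treats a whole bedroom, so participants who share a room on opposite sequences can lose the purifier contrast

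*Combined protocol and SAP*

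**What the plan says.** Study Aim 1 is a two-period crossover: "It will be a prospective, randomized cross over study in which participants will act as their own control". Under Design and Method, allocation follows consent: "After screening and obtaining informed consent, they will be randomized to either intervention arm or control arm". The section Screening, recruitment and randomization adds only this: "Participants will be randomized using sealed, opaque envelopes". No household or room is named as a unit, and nothing ties the sequence or start date of people who live together.

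The purifier acts on a room. The section Intervention group states: "The purifier will be placed in their bedroom or in the room where participants sleep at night". Every purifier has the same clock window: "to be used daily for 12 hours between 8 PM and 8 AM". The control device is the same purifier without its filter. The mask, by contrast, is personal and worn outdoors.

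Both disease arms require a closed sleeping space: "Individuals who sleep in a closed space (such as a bedroom) for minimum of 6 hours/daily". The section Pollution measurement and recording treats that place as the exposure site: the team "will record the indoor air pollution level at the site where participants sleep at night". The inclusion and exclusion lists set no limit on participants per room or household.

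On analysis, the plan specifies intention to treat and then: "Marginal (GEE) models will be used to analyze the data". The clustering unit is not named.

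**The concern.** The unit that is randomised (a person) differs from the unit that one of the two interventions treats (a room). Recruitment is local and the first screening visit is at home, so a health worker may meet two eligible adults under one roof. One may have hypertension and the other diabetes, so a pair can straddle the two arms.

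Suppose two such people share a bedroom, start on the same day and draw opposite sequences. In each period one filtered and one unfiltered purifier run in that room. Both people breathe filtered air in both periods, and their within-person purifier contrast is zero. A crossover usually protects a within-person comparison, but here both members' control periods are exposed. Intention to treat keeps these people in the analysis, so the estimated effect shrinks. Only 15% of participants are selected for indoor monitoring, so most affected rooms would go unmeasured.

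**Working it through.** **Inputs from the protocol** (Sample size and power calculation; Design and Method; Washout period)
- Hypertension: n = 128, difference 2 mmHg, SD 8, so d = 2/8 = 0.25.
- Diabetes: n = 33, difference 10 mg/dL, SD 20, so d = 10/20 = 0.5.
- Alpha 0.05, power 80%. Two-sided testing, with the SD read as that of the within-person difference, reproduces the plan.
- Timing: 4 weeks, 2-week washout, 4 weeks.

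**Assumed, because the documents are silent**
- 1:1 allocation to sequence, drawn independently, and at most two participants per room.
- h = share of participants sleeping in a room with another participant.
- s = share of the total effect due to the purifier (1 is the upper bound; 0.5 is also shown).
- The loss is proportional to the weeks of overlap, and the SD is unchanged.

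**Step 1: the plan's own figures.** The normal approximation n = ((1.960 + 0.842) × SD/difference)² gives 125.6 (hypertension) and 31.4 (diabetes). The exact paired t calculation gives 128 and 34. At the stated 128 and 33, power is 80.2% and 79.5%. The stated sizes are sound, but they leave no margin for dilution.

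**Step 2: how much of a control period is exposed.** Let L be the weeks between the two start dates.
- Opposite sequences (probability 0.5): a fraction max(0, 1 − L/4) of each member's control period is exposed.
- Same sequence (probability 0.5): a fraction max(0, 1 − |L − 6|/4) of one member's control period is exposed. This is above zero for L between 2 and 10, and complete at L = 6.

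The mean exposed fraction per room-sharer is f = 0.5 × max(0, 1 − L/4) + 0.25 × max(0, 1 − |L − 6|/4).

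| L (weeks) | 0 | 1 | 2 | 4 | 6 | 10 |
|---|---|---|---|---|---|---|
| f | 0.5 | 0.375 | 0.25 | 0.125 | 0.25 | 0 |

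Staggered starts reduce the problem but do not remove it.

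**Step 3: diluted effect and power.** The effect is multiplied by m = 1 − s × h × f. Power is two-sided paired-t power (noncentral t) at d × m. For example, h = 10%, s = 1, f = 0.5 gives m = 1 − 0.05 = 0.95, so 2.0 mmHg becomes 1.90.

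Concurrent periods (f = 0.5), power hypertension / diabetes:

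| h | Purifier = whole effect | Purifier = half the effect |
|---|---|---|
| 0 | 80.2% / 79.5% | 80.2% / 79.5% |
| 2% | 79.4% / 78.7% | 79.8% / 79.1% |
| 5% | 78.1% / 77.5% | 79.2% / 78.5% |
| 10% | 76.0% / 75.4% | 78.1% / 77.5% |
| 20% | 71.4% / 70.8% | 76.0% / 75.4% |

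In the whole-effect column, the 2.0 mmHg difference becomes 1.98, 1.95, 1.90 and 1.80 at h = 2%, 5%, 10% and 20%.

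With starts 2 weeks apart (f = 0.25) and the purifier as the whole effect, power is 78.1% / 77.5% at h = 10% and 76.0% / 75.4% at h = 20%.

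**Step 4: price of allocating by room.** Room-mates on one sequence give correlated differences, with design effect 1 + h × ICC. For h from 5% to 20% and an assumed ICC from 0.05 to 0.30:
- Hypertension: 128 × 1.0025 = 128.3, so 129, up to 128 × 1.06 = 135.7, so 136.
- Diabetes: 33 × 1.0025 = 33.1, so 34, up to 33 × 1.06 = 34.98, so 35.

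With no added participants, h = 10% and ICC 0.30, power is 79.0% / 78.4%. Individual allocation gives 76.0% / 75.4% (whole effect) or 78.1% / 77.5% (half).

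**The case against.** The strongest reply is that the problem may not arise. The documents do not say that any participants share a room. Two room-mates would each have to be already diagnosed, stable for 3 months, within the blood pressure or glucose window, non-smoking and adherent in the run-in, and then have overlapping periods. Screening forms 0 and 1 are not in the supplied text and may record household or bedroom. A home visit would also make sharing visible. All of this stands and limits the likely size, but none of it is a written rule.

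The loss is also small at low sharing. For hypertension at h = 5% it is 80.2 − 78.1 = about 2 points at the upper bound and 1 point if the purifier gives half the effect. With concurrent starts and the whole effect, power drops below 75% only when h exceeds about 12% (hypertension) or 11% (diabetes). The bias is towards no effect, so it cannot by itself create a false positive. That also stands.

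Room-level allocation is not free of trouble. One member may have to wait for the other, a room-mate found late cannot start on the same dates, and two filtered purifiers would stand in one room. At h = 5%, ICC 0.30 and half the effect, it gives 79.6% against 79.2% for hypertension, a gain of under half a point. These objections are fair, but they do not touch the one-participant-per-bedroom option.

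Finally, treating the loss as proportional to weeks of overlap is a simplification. Readings are taken at day 0, week 2 and week 4, so when the overlap falls matters too.

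**Conclusion.** The concern holds, as a conditional one. Followed as written, the plan allows room-mates to be placed on opposite sequences, and with overlapping periods the purifier contrast for such pairs is partly or wholly lost. The effect is then underestimated and power falls below the 80% target.

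The size is unknown because h is not given: no loss at h = 0, less than one point at h = 2%, and roughly 4 to 9 points at h = 10% to 20% with concurrent periods and the purifier as the whole effect. If the purifier gives half the effect, the last range is about 2 to 4 points. These figures rest on the assumed sharing, 1:1 allocation and proportional loss. The stated sample sizes are not in error. Confidence is medium, because the screening forms could not be seen. The change is worth making before enrolment, since no later analysis can restore a contrast that was never created.

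**What to change.** Choose one rule and write it into Screening, recruitment and randomization.

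1. **One participant per bedroom.** Add this as an eligibility rule covering both disease arms together. Sample size and analysis stay as they are. The cost is some eligible recruits.
2. **One envelope per shared bedroom (or household).** All participants in that unit, in either disease arm, follow the same sequence on the same dates. Common dates are essential, because same-sequence pairs with staggered starts can still overlap. Name the unit as the GEE cluster in the Analysis section. In the assumed range this needs 129 to 136 participants with hypertension and 34 to 35 with diabetes to hold power. The design effect is slightly pessimistic, because pairs split across the two disease arms add no correlation within either analysis. The protocol would also need to say how late-found room-mates and two purifiers in one room are handled.

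The first option is the simpler one. Under either, recording at screening whether a participant shares a bedroom with another participant would show how large h is.
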